## Which IRB

 Medical  NonMedical

## Protocol Process Type

 Exemption  
 Expedited (Must be risk level 1)  
 Full

**IMPORTANT NOTE:** You will not be able to change your selections for "Which IRB" and "Protocol Process Type" after saving this section. If you select the wrong IRB or Protocol Process Type, you may need to create a new application.

See below for guidance on these options, or refer to ORI's "[Getting Started](#)" page. Please contact the Office of Research Integrity (ORI) at [contact] with any questions prior to saving your selections.

**\*Which IRB\***

The **Medical IRB** reviews research from the Colleges of:

- Dentistry
- Health Sciences
- Medicine
- Nursing
- Pharmacy and Health Sciences
- and Public Health.

The **Nonmedical IRB** reviews research from the Colleges of:

- Agriculture
- Arts and Sciences
- Business and Economics
- Communication and Information
- Design; Education
- Fine Arts
- Law
- and Social Work

**Note:** Studies that involve administration of drugs, testing safety or effectiveness of medical devices, or invasive medical procedures must be reviewed by the **Medical IRB** regardless of the college from which the application originates.

**\*Which Protocol Process Type\***

Under federal regulations, the IRB can process an application to conduct research involving human subjects in one of three ways:

- by exemption certification
- by expedited review.
- by full review;

The investigator makes the preliminary determination of the type of review for which a study is eligible. Please refer to ORI's "[Getting Started](#)" page for more information about which activities are eligible for each type of review.

The revised Common Rule expanded exemption certification category 4 for certain secondary research with identifiable information or biospecimens. The regulations no longer require the information or biospecimens to be existing. For more information see the [Exemption Categories Tool](#).

**PROJECT INFORMATION****0 unresolved  
comment(s)**

Title of Project: (Use the exact title listed in the grant/contract application, if applicable).

If your research investigates any aspect of COVID-19, please include "COVID19" at the beginning of your Project Title and Short Title

Investigating the impact of Moringa oleifera leaf supplementation on growth, nutrition, and inflammation in Kenya: an acceptability and pilot RCT

**Short Title Description**

Please use a few key words to easily identify your study - this text will be displayed in the Dashboard listing for your study.

Moringa Kenya Pilot

Anticipated Ending Date of Research Project: 12/30/2022

Maximum number of human subjects (or records/specimens to be reviewed) 104

After approval, will the study be open to enrollment of new subjects or new data/specimen collection?  Yes  No

**SUBJECT DEMOGRAPHICS**

0 unresolved comment(s)

Age level of human subjects: (i.e., 6 mths.; 2yrs., etc.)  to **Study Population:**

Describe the characteristics of the subject population, including age range, gender, ethnic background and health status. Identify the criteria for inclusion and exclusion.

Provide the following information:

- A description of the subject selection criteria and rationale for selection in terms of the scientific objectives and proposed study design;
- A compelling rationale for proposed exclusion of any sex/gender or racial/ethnic group;
- Justification for the inclusion of vulnerable groups such as children, prisoners, adults with impaired consent capacity, or others who may be vulnerable to coercion or undue influence.

Please consider these resources:

[NIH Diversity Policy](#)

[FDA Diversity Guidance](#) 

**Phase A) Acceptability**

Inclusion lactating women 18 years or over, children 6-59 months.

Exclusion inability to feed orally

We anticipate enrolling 10 adults including lactating women and 10 children. All participants will be Kenyan and residing in the region of Kisumu.

**Phase B) Pilot RCT**

Inclusion criteria: lactating women of at least 18 years of age and their exclusively breastfed infants within 30 days of delivery with informed consent. Children 6-59 months who are orally feeding with caregiver informed consent.

Exclusion criteria: regular maternal consumption of moringa in the month prior to study enrollment, receipt and consumption of food supplementation program, or inability to feed orally; for infant, significant congenital disease, inability to feed orally. For child: inability to feed orally or refusal to eat porridge (>3 days consecutively).

We anticipate enrolling up to 50 mother-infant dyads in each of two arms and 50 children in each of two arms.

We propose starting enrollment as soon as all ethical approvals obtained, personnel hired, and study supplies obtained; there is no additional sample composition of subjects. This study targets women and infants as breastfeeding infants have the potential to receive the greatest benefit from moringa leaf supplementation to their lactating mothers.

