**Relevance to Kisumu, Kenya:** Our target subjects of Kisumu, Kenya are a rural population with poor water, sanitation, hygiene, high rates of undernutrition and limited access to health resources. They have low Dietary Diversity (availability of adequate varied food groups) leading to additional micronutrient deficiencies. They are mostly subsistence farmers who are not universally acquainted with *moringa* cultivation or consumption, however we have recently completed a study in Kisumu that shows excellent acceptance and uptake of *moringa* intensive leaf cultivation and a positive attitude to dried leaf powder consumption ([name] and [name], manuscript in progress 2020). The wider Kisumu population is the target area of our partner Pamoja Community Based Organization (Pamoja, executive director [name]), which spans three districts in the region of Kisumu comprising some of the highest-needs populations in Kenya. In a 2019 baseline survey of 469 0-59 month old children within Pamoja's catchment area, 25% were stunted, 8% wasted, and 13% underweight (unpublished data, personal communication from [name]). Micronutrient deficiencies are not specifically defined in this population, however an estimated 69% of children under five years in Kenya are iron deficient and 20-39% are estimated to have vitamin A deficiency. Targeting undernutrition in a cost-effective manner is crucially needed in this region; our study will work with the infrastructure and trust of Pamoja and the communities it serves by testing acceptability of *moringa* leaf consumption in staple food of grain porridge, acceptability of placebo, and conducting a pilot of *moringa* leaf consumption and its effect on childhood growth, nutrition, and intestinal and systemic inflammation.

**Safety:** No trial of *moringa* leaf consumption in children or lactating women has shown significant adverse effects. Cultures all over the world and across centuries have used *moringa* leaf as food and medicine without reported ill effect at traditional doses. Seed, root, or leaf extract are not the intervention used in this study. They concentrate the biochemically active plant isothiocyanates and phytosterols

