### We will implement:

A) a short acceptability study of acceptability, adherence, and preference for moringa dried leaf consumption and placebo consumption in porridge. Selection will be from lactating women 18 years and over and children 6-59 months; subjects will come from our target region of Kisumu.

B) a pilot placebo-controlled RCT of mother-infant dyads and their children 6-59 months who present for first postnatal check to two high volume rural maternal and child health centers in Kisumu, Kenya.

Inclusion criteria: lactating women of at least 18 years of age and their exclusively breastfed infants within 30 days of delivery with informed consent. Children 6-59 months of age who are eating food.

Exclusion criteria: regular maternal consumption of moringa, receipt and consumption of food supplementation program, or inability to feed orally; for infant, significant congenital disease, inability to feed orally. For mother or child: inability to orally feed or complete refusal (>3 days) to eat moringa or placebo porridge.

Sample size: 100 infant-mother pairs in each arm (n=400 participants total). 100 children in each arm (n=200)

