### Intervention:

Mothers: 20g moringa leaf powder vs. placebo in the staple food of porridge consumed daily for three months. Children: 10g moringa leaf powder vs. placebo in porridge consumed daily for three months. Moringa dose will be determined by the upper limit of acceptability in Phase A.

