### Data collection:

Monthly anthropometrics for mother, infant, and child. These include infant weight, length and maternal and child weight, height/length, and mid-upper arm circumference.

Enrollment and exit quantitative surveys including but not limited to Food Frequency Questionnaire from which we will calculate Dietary

Diversity Score.

Mother, infant and child finger or finger/ heel stick for hemoglobin and capillary blood collection at study enrollment and exit.

Mother, infant and child feces collection at study enrollment and exit.

Daily recording by parent in provided diary of daily moringa percent consumption, incidence of diarrhea, diagnosis by health professional of medical condition in mother, infant, or child.

Lactating Women:

24 hour volume of breastmilk at study enrollment and exit

Breastmilk sample collection (est. 5ml) at study enrollment and exit

We would like to complete one more anthropometric measurement (weight and length) of enrolled infants in the next few months; this is 8-12 months from study start.

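### The prior-moringa exclusion covers mothers only, so a child aged 6-59 months who already eats moringa can be randomised to a comparison of the child's own moringa intake.

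*Combined protocol and SAP*

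**What the plan says.** Eligibility for the pilot RCT is set out twice.

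- **Study Population, Phase B.** Children enter under "Children 6-59 months who are orally feeding with caregiver informed consent", with no condition on diet. The opening exclusions include "regular maternal consumption of moringa in the month prior to study enrollment, receipt and consumption of food supplementation program". Separate lists follow for the infant and the child, and the child's reads "For child: inability to feed orally or refusal to eat porridge (>3 days consecutively".
- **Study Design.** The opening list is "regular maternal consumption of moringa, receipt and consumption of food supplementation program, or inability to feed orally", now without the one-month window. The later entry is "For mother or child: inability to orally feed or complete refusal (>3 days) to eat moringa or placebo porridge".

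The Intervention section gives children their own contrast: "Children: 10g moringa leaf powder vs. placebo in porridge consumed daily for three months". Aim 2 tests that contrast for the children's own growth and nutritional status.

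On intake, Data collection specifies "Daily recording by parent in provided diary of daily moringa percent consumption", plus a Food Frequency Questionnaire at enrolment and exit. Research Procedures, Phase B, describes a monthly review based on diary amounts and on inspecting how much porridge and powder is left.

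On local use, the Background says "we have recently completed a study in Kisumu that shows excellent acceptance and uptake of" intensive moringa leaf growing. The same sentence says that familiarity with moringa is not universal there.

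**The concern.** Whoever eats the assigned product is the person whose background moringa intake can blur the comparison. In the mother-infant part that person is the mother, and the plan screens her. In the child part it is the child, and the plan does not screen the child. The documents give no reason for the difference.

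A child with regular prior intake brings that exposure into the baseline vitamin A, iron and stool markers. If intake continues in the placebo arm, the control group is partly treated. A null child result could then mean either that moringa has no effect or that the arms differed less in exposure than planned, and the data described would not clearly separate the two.

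**Working it through.** **1. Does either child list contain a moringa item?**

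| Item | Study Population, Phase B | Study Design |
|---|---|---|
| Prior moringa | Maternal, month before enrolment | Maternal, no window |
| Food programme | No person named | No person named |
| Child's own list | Oral feeding; refusal of porridge | Oral feeding; refusal of study porridge (shared with mother) |

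Both versions restrict the moringa item to the mother by name, and neither child list has one. Followed as written, the criteria admit a child who regularly eats moringa.

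**2. Does the food-programme item cover children?** It sits in the opening list beside the maternal moringa item. In Study Population the oral-feeding item recurs under each person, which suggests that the opening list is for mothers. In Study Design the same item stands in the opening list and again under a joint heading for mother or child, so repetition does not show whom the opening list covers. The text leaves the question open.

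**3. Is background intake measured in another way?** The questionnaire describes diet at enrolment and exit, but no eligibility rule is tied to it, and the text does not say whether it asks about moringa. The diary and monthly review are described in terms of study porridge and powder. The SAP names no adjustment or stratification for background moringa intake.

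**4. Illustration of size.** The plan has no power calculation for children, so there is no figure to reproduce; its one sample-size calculation concerns infant stunting. Inputs:

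- Alpha 0.05 (SAP), taken as two-sided because sidedness is not stated.
- Starting power 80%, assumed for children.
- A share *c* of placebo children with exposure equivalent to the study moringa, assumed at 10%, 20% and 30%.

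If a share *c* of controls respond as if treated, the mean difference becomes (1 − *c*) times its full size. Any change in the SD is ignored. At 80% power the standardised difference is 1.96 + 0.84 = 2.80, so

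power = Φ((1 − *c*) × 2.80 − 1.96).

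| *c* | (1 − *c*) × 2.80 − 1.96 | Power |
|---|---|---|
| 10% | 0.56 | 71% |
| 20% | 0.28 | 61% |
| 30% | 0.00 | 50% |

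The loss is the same at 50 children per arm (Study Population) and at 100 per arm (Study Design), because the starting power is fixed at 80%. The sample size changes only the difference that corresponds to 80%: 2.80 × √(2/50) = 0.56 SD, or 2.80 × √(2/100) = 0.40 SD.

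**The case against.** The other side has several fair points.

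- **Household link.** Study Design describes the children as those of the enrolled mothers, and under the recruitment section the mother consents for her infant and child. Screening her may remove some moringa-eating households. This stands in part: it does not test the child's own intake, and recruitment also takes place at well child checks.
- **Diet is measured.** The questionnaire may capture moringa, and the attached data-collection tools are not reproduced in the text. That may help interpretation, but it is not a screen and falls only at the two ends of follow-up.
- **Prevalence is unknown.** The Background reports uptake of growing and a favourable attitude to eating the powder, not intake, and nothing about children. A reader might infer that moringa was recently promoted in these clinics' catchments and that many children eat it daily. The documents support neither inference.
- **The food-programme rule.** A reader might infer that it too is for mothers only. The wording does not settle this, and the power figures do not model it: programme food would leave less room to respond rather than give controls moringa.
- **Bias.** A reader might infer a directional bias. Randomisation should balance prior use in expectation, so the documents do not support that.
- **A secondary part of a pilot.** The demographics section makes child enrolment depend on extended funding, and the stated efficacy hypothesis names infants. This lowers the stakes, but Aim 2 still includes children.

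**Conclusion.** The gap is real for moringa: both statements of the criteria limit the exclusion to maternal consumption, and a child who regularly eats moringa can be randomised. For the food programme the finding is ambiguity, not omission.

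The consequence is reduced contrast and a null result that is harder to read. Its size cannot be taken from the documents. The fall from 80% to between 71% and 50% rests on an assumed 10-30% of placebo children with fully equivalent exposure and on a starting power that the plan never states for children. Lighter household intake would dilute less. The figures show how power responds to dilution and are not an estimate for this trial.

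**What to change.** 1. Add regular moringa consumption by the child in the month before enrolment to the child exclusions in both Study Population (Phase B) and Study Design. Align the two maternal versions on whether the one-month window applies.
2. State in both places whether the food-programme exclusion applies to children.
3. At the month 1, 2 and 3 visits, ask mothers and children in both arms one question on non-study moringa eaten since the last visit, and report the answers by arm.

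If children have already been enrolled, report background moringa intake at enrolment and exit by arm wherever the questionnaire recorded it.

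The cost is protocol wording, one extra question at existing visits, and the loss of otherwise eligible children in proportion to how common prior use is. That loss is small if use is rare, but would approach 30% of children if use were as common as the top of the illustrated range.

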**Attachments**

Indicate the targeted/planned enrollment of the following members of minority groups and their subpopulations. Possible demographic sources: [Census Regional Analyst Edition](#), [Kentucky Race/Ethnic Table](#), [Kentucky Population Data](#).

(Please note: The IRB will expect this information to be reported at Continuation Review time for Pre-2019 FDA-regulated Expedited review and Full review applications):

Participant Demographics				
	Cisgender Man 	Cisgender Woman 	TGNB/TGE 	Unknown/Not Reported
American				
Indian/Alaskan Native:				
Asian:				
Black/African American:				
Latinx:				
Native Hawaiian/Pacific Islander:				
White:				
American Arab/Middle Eastern/North African:				
Indigenous People Around the World:				
More than One Race:				
Unknown or Not Reported:				

If unknown, please explain why:

also children if funding extended. Therefore the majority of participants will be female.

Indicate the categories of subjects and controls to be included in the study. You may be required to complete additional forms depending on the subject categories which apply to your research. If the study does not involve direct intervention or direct interaction with subjects, (e.g., record-review research, outcomes registries), do not check populations which the research does not specifically target. For example: a large record review of a diverse population may incidentally include a prisoner or an international citizen, but you should not check those categories if the focus of the study has nothing to do with that status.

Check All That Apply (at least one item must be selected)

**ADDITIONAL INFORMATION:**

- Children (individuals under age 18)
- Wards of the State (Children)
- Emancipated Minors
- Students
- College of Medicine Students
- UK Medical Center Residents or House Officers
- Impaired Consent Capacity Adults
- Pregnant Women/Neonates/Fetal Material
- Prisoners
- Non-English Speaking (translated long or short form)
- International Citizens
- Normal Volunteers
- Military Personnel and/or DoD Civilian Employees
- Patients
- Appalachian Population

Please visit the [IRB Survival Handbook](#) for more information on:

- Children/Emancipated Minors
- Students as Subjects
- Prisoners
- Impaired Consent Capacity Adults
- Economically or Educationally Disadvantaged Persons

Other Resources:

- UKMC Residents or House Officers [see [requirement of GME](#)]
- [Non-English Speaking](#) [see also the E-IRB Research Description section on this same topic]
- [International Citizens](#) [DoD SOP may apply]
- [Military Personnel and/or DoD Civilian Employees](#)

**Assessment of the potential recruitment of subjects with impaired consent capacity (or likelihood):**

Check this box if your study does NOT involve direct intervention or direct interaction with subjects (e.g., record-review research, secondary data analysis). If there is no direct intervention/interaction you will not need to answer the impaired consent capacity questions.

Does this study focus on adult subjects with any conditions that present a high *likelihood* of impaired consent capacity or *fluctuations* in consent capacity? (see examples below)

Yes  No

If Yes and you are not filing for exemption certification, go to ["Form T"](#), complete the form, and attach it using the button below.

**Examples of such conditions include:**

- Traumatic brain injury or acquired brain injury
- Severe depressive disorders or Bipolar disorders
- Schizophrenia or other mental disorders that involve serious cognitive disturbances
- Stroke
- Developmental disabilities
- Degenerative dementias
- CNS cancers and other cancers with possible CNS involvement
- Late stage Parkinson's Disease
- Late stage persistent substance dependence
- Ischemic heart disease
- HIV/AIDS
- COPD
- Renal insufficiency
- Diabetes
- Autoimmune or inflammatory disorders
- Chronic non-malignant pain disorders
- Drug effects
- Other acute medical crises

Attachments

SUBJECT CHILDREN

0 unresolved  
comment(s)**SECTION 1. Risk Level**

Complete this section and include it with your IRB application submission. *In Kentucky, a child is an individual less than 18 years of age unless the individual is legally emancipated.*

Note: the explanation(s) you are being asked to provide in Section 1 correlate(s) to the risk level you selected in the Risk Level section.

**Minimal risk means that the probability and magnitude of the harm or discomfort anticipated in the research are not greater in and of themselves than those ordinarily encountered in daily life of a healthy child or during the performance of routine physical or psychological exams or tests.**

**FOR FDA REGULATED RESEARCH:** Based on the 2013 FDA final rule Subpart D, a placebo control arm of a clinical trial must be approved under either [Risk Category 1](#), [Risk Category 3](#), or [Risk Category 4](#). FDA does not consider administration of a placebo to offer a prospect of direct benefit to an individual subject under Subpart D, Risk Category 2 [[21 CFR 50.52](#)].

**Not involve greater than minimal risk.**

In the Risk Level section of the IRB Application you indicated your research does not involve greater than minimal risk.

A. Explain why your research does not involve greater than minimal risk:

Risks are: discomfort and bleeding or bruising from capillary stick. Infants and children receive this as a routine physical test in their lifetimes. This is a routine test for newborn screening at birth and again for blood sugar checks if blood sugars are low and again for hemoglobin assessment between 12-24 months of age.

Additional risks are bloating and/or diarrhea from the consumption of moringa or the placebo; both contain a lot of soluble fiber.

Additional risks are not liking the taste of moringa or placebo.

